#### Cost Data

Cost data will be analysed using parametric and non-parametric statistical methods which explicitly allow for the censoring of (indirect & total) costs at 28 days, i.e. for those patients who are not discharged from hospital within 28 days and thus enable an unbiased assessment of potential cost differences between the three diagnostic groups to be made. Estimation of the cost distribution over longer timescales will make use of extrapolation techniques using time of discharge obtained from hospital information systems.

	Study Day			
	Admission	Days	Day 28	
Assessments	(Day 1)	2, 3, 4, 7 ( + 1), & 10 ( + 1)	( + 2)	
Pre-study assessment by admitting medical team	✓			
Note time of admission (CRF)	$\checkmark$			
Inclusion/Exclusion criteria check (CRF)	~			
Written informed Consent (or Assent) (CRF)	~	✓ (Consent upon recovery)		
Demography/immunisation status check (CRF)	~			
Medical history/concomitant medications check (CRF)	~			
Symptom assessment (CRF)	~			
Clinical findings, including body weight and temperature (CRF). Establish when patient first becomes apyrexial ( $\leq$ 37.2°C), requires supplemental O 2 , and remains so for >24 hours (CRF)	1	✓ (temperature, O 2 )		
EuroQol. Quality of Life assessment (CRF)				
MRC Dyspnoea Scale	~			
Physical Activity Questionnaire		✓		
Diagnostic studies ordered by the admitting medical team (CRF)	~	$\checkmark$		
Collection of trial specific diagnostic specimens (CRF):	~	✓ (antibody, Day 10- 90)		
Nasopharyngeal (Quidel & virus culture) Nasopharyngeal Swabs Sputum (Gram stain & culture) Urine (Binax NOW) Blood (Blood cultures, serum antibodies)		Day 2-3 if first swabs positive if available.		
Record time when diagnostic test results were made available to the ward nurses, and/or admitting team (CRF)	~	4		
Record antimicrobials & antivirals (identity,route, dose, time of administration) prescribed by admitting medical team (CRF)	~			
Note the time of any changes in antimicrobials & antivirals (identity,route, dose, time of administration) prescribed by admitting medical team (CRF)		1		
Bed location, i.e., record bay or a single room (CRF)	~			
Note time of any subsequent change in isolation status (CRF)		$\checkmark$		
ITU and ventilatory support: Document whether admitted or required ventilatory support (CRF)	~	¥		
Date of hospital discharge/ Death within 28 days of admission (CRF)		✓		
Discharge diagnosis (CRF)		✓		

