the different microbiological tests for influenza, RSV, and *S. pneumoniae*, together with the results, will be documented

*Treatment* The nature (name, dose, frequency, and route of administration) of all antimicrobials given to all patients within 10 days of admission will be documented. Note will be made of when 'broad-spectrum' treatment is switched to 'narrow-spectrum treatment'; when intravenous antibiotics are switched to oral therapy; and when antibiotics are discontinued. The requirement for supplemental oxygen will also be documented.

*Isolation status, admission to ITU, and ventilatory support* A record will be kept of (i) the patient's isolation status during the first 7 days of admission, and whether the patient was admitted to an ITU and/or required ventilatory support (including ward-based CPAP) during the first 10 days of admission.

*Pyrexia* The time (24 hr clock and date) during the patient's first 10 days of hospitalisation (or until death, if relevant) when the patient first became apyrexial (temperature  $\leq 37.2^{\circ}$ C), and remained so for a period of >24 hours will be recorded.

*Convalescent serology* A convalescent blood sample will be collected for paired acute and convalescent serology for influenza and RSV at 10 -90days.

*Diagnostic studies* The nature and results of all diagnostic studies (e.g., chest radiograph, ECG, full blood count, cardiac enzymes, PaO2) carried out by the medical team will be recorded.

*EuroQol* The health status of all patients will be assessed by the EuroQol on days 7 and 28. Where patients have been discharged the EuroQol will be assessed by telephone interview of the patient or by postal questionnaire or by proxy (Appendix I).

*Humoral and cell-mediated immunity to the pneumococcus.* Patients whose antigen tests for the pneumococcus are positive and an equivalent number of people whose pneumococcal test is negative will be bled on one occasion only within 5 days of hospital admission, for tests of cellular and humoral immunity to the pneumococcus.

Physical Activity Questionnaire will be completed on day 2 or 3.

*Deaths* Deaths that occur within a maximum 28 days of hospitalisation will be identified by the study nurse and recorded in the CRF. [Note: the principal investigator MUST be notified by the study nurse of all deaths that occur within 28 days of admission and of the patient's study group].

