#### 6.1.6 Demography/immunisation status

Demographic data including details of residential status, smoking habits, alcohol consumption, household contacts, immunisation status (influenza and pneumococcus during the previous 3 years), and hospital admissions during the period  $1^{st}$  September –  $30^{th}$  April of the previous winter will be recorded in the CRF.

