#### 6.2.12 Convalescent serology (Day 10-90)

A 10ml convalescent blood sample will be collected from survivors at **10-90** days. The serum will be saved for paired acute and convalescent serology for influenza and RSV. The blood sample will be labelled with the participant's details, including name, date of birth, hospital number, and date of collection, AND in addition with the participant's unique trial code corresponding to the sequentially numbered study pack. The blood sample will be transported to the laboratory using the UHL transport system.

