#### 7.3 Definitions of influenza, RSV and S. pneumoniae positivity

Influenza positive Patients will be considered influenza positive if:

- The Quidel QuickVue Influenza A and B test is positive, and/or
- The multiplex PCR is positive, and/or
- Viral culture is positive, and/or
- Serology results indicate influenza infection (e.g., 4-fold increase in influenza A H3N2, H1N1, or influenza B HI antibody from acute to convalescent sera).

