#### **RSV positive** Patients will be considered RSV positive if:

The multiplex PCR is positive, and/or

- Viral culture is positive, and/or
- Serology results indicate RSV infection (e.g., ≥4-fold increase in RSV antibodies from Day 1 to Day 30).

S. pneumoniae positive Patients will be considered influenza positive if:

- The Binax NOW S. pneumoniae antigen test is positive, and/or
- Blood culture is positive, and/or
- Sputum culture is positive, AND the sputum sample is macroscopically purulent, AND the sputum sample reveals increased numbers of polymorphonuclear leucocytes, AND the Gram stain is positive, AND there is moderate-to-high amounts of growth, according to criteria used by the laboratory.

Evaluations will be based on: (i) populations whose cardio-pulmonary illness is confirmed as due to influenza, RSV or *S. pneumoniae*, and (ii) the study groups comprising all people who are investigated by the different strategies under investigation (rapid near patient tests, *versus* rapid molecular diagnosis, *versus* conventional laboratory tests).

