#### We would also like to ask you a few simple questions about your health today.

**Question 1**. Firstly, we would like to ask you if any of the following health care professionals have visited you in your own home since you were discharged from hospital? Remember, here we are only interested in health care you have received in your own home. Have you seen a PLEASE READ OUT THE LIST BELOW: IF YES, ASK How many times did you see this person?

$\Box_1$	GP	How many times?
$\square_2$	District nurse	How many times?
3	Practice nurse	How many times?
4	Other nurse	How many times?
5	Home care worker/ home help	How many times?

**AT END of LIST ASK**. Apart from the people I have mentioned have you any other health care professionals in your own home? **IF YES, ASK**: How many times did you see this person? **PLEASE KEEP ASKING UNTIL RESPONDENT STATES THEY HAVE SEEN NO OTHER HEALTH CARE PROFESSIONAL**.

6	Other person (please specify)	How many times?
7	Other person (please specify)	How many times?
8	Other person (please specify)	How many times?

**Question 2.** We would now like you to think of any health care professionals that you might have seen outside your own home since you were discharged from hospital. Remember, here we are only interested in health care you have received outside your own home. Have you seen a **READ OUT THE LIST BELOW: IF YES, ASK** How many times did you see this person?

1	Hospital doctor in outpatients department	How many times?
$\square_2$	GP	How many times?
3	Practice nurse	How many times?
4	Other nurse	How many times?
5	A&E department	How many times?

Apart from the people I have mentioned have you visited any other health care professionals outside your home? IF YES, ASK: How many times did you see this person? PLEASE KEEP ASKING UNTIL RESPONDENT STATES THEY HAVE SEEN NO OTHER HEALTH CARE PROFESSIONAL.

6	Other (please specify)	How many times?
7	Other (please specify)	How many times?
8	Other (please specify)	How many times?

**Question 3.** Since your discharge from hospital have you had any extra medicines prescribed for you? Please do not include any medicines you were prescribed in hospital, or any medicines that you regularly received before your stay in hospital. We are only interested in extra medicines that have been prescribed since you were discharged from hospital.

Yes	$\Box_1$
No	$\square_2$

IF YES, ASK How many new medicines have you been prescribed? \_\_\_\_\_

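### Section 7.3 lets a four-fold HI rise up to day 90 define influenza on its own, so a vaccine response or a later infection can be counted as an index influenza case

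*Protocol*

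**What the plan says.** Section 7.3 lists four criteria for influenza: QuickVue, multiplex PCR, culture and serology. They are alternatives, as the link "Viral culture is positive, and/or" shows. The serological criterion reads "Serology results indicate influenza infection (e.g., 4-fold increase in influenza A H3N2, H1N1, or influenza B HI antibody from acute to convalescent sera". It sets no interval between the sera and no condition on vaccination.

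Section 4.1 fixes the timing of the second sample: "A convalescent blood sample will be collected for paired acute and convalescent serology for influenza and RSV at 10 -90days". Section 6.2.12 gives the same window and the same purpose: "The serum will be saved for paired acute and convalescent serology for influenza and RSV". For RSV, Section 7.3 gives a different example, a rise in "antibodies from Day 1 to Day 30".

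Section 6.1.6 records "immunisation status (influenza and pneumococcus during the previous 3 years" at entry. In the schedule of assessments the row "Demography/immunisation status check (CRF" is ticked for admission only. The day-28 questionnaires in Appendix I ask about health-care contacts and medicines, for example "Since your discharge from hospital have you had any extra medicines prescribed for you", and have no vaccine item. Recent vaccination is not an exclusion in Section 5.3. Enrolment opens on 1 September each year (Section 5.1).

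**The concern.** HI antibody rises after vaccination as well as after infection. A patient vaccinated between the sera, or so shortly before admission that the response is still building, can show a four-fold rise without having had influenza. Separately, a patient who catches influenza weeks after discharge can show a true rise that has nothing to do with the admission under study. Section 7.3 intends its evaluations for patients whose presenting illness was due to the pathogen, and neither of these patients fits.

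The influenza-positive set is used in:
- time to stopping antibiotics, neuraminidase-inhibitor use and isolation (Section 7.5.1);
- the influenza subset analyses of length of stay, quality of life and cost (Sections 7.5.1 and 7.5.2);
- the influenza admission rate (Section 7.5.4);
- diagnostic accuracy, to the extent that serology enters the comparator (Section 7.5.3).

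A patient without influenza at admission should be negative on QuickVue, PCR and culture. A rapid result cannot change that patient's care through an influenza diagnosis. Each such patient pulls a subset comparison towards no difference and looks like a missed case wherever serology is the reference.

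**Working it through.** **1. Can the affected patients be identified?** Set the data collection beside the serum window.
- Vaccination before admission: status over 3 years is recorded on day 1. The protocol does not say that a date is taken, and no rule uses the answer.
- Vaccination after admission: no item asks about it. The last questionnaire is at day 28 and the last permitted serum at day 90, so 90 − 28 = 62 days pass with no planned enquiry.
- Infection after the index admission: nothing in the criterion separates it from the index illness.

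**2. The plan's own case count.** From Section 7.1 and the synopsis: 666 × 11.57 = 7705.6; × 5/7 = 5504; × 2/3 = 3669; × 3/4 = 2752 elderly patients. At 10% influenza, 0.10 × 2752 = 275.2, which matches the stated 275.

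**3. Illustration of size.** The documents give no figure for paired-serum completeness, vaccination between sera or response to vaccine. The ranges below are assumptions: paired sera in 50–80%, vaccinated between sera 2–20%, four-fold rise after vaccine 30–70%.

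False cases F = 2752 × 0.90 × paired × vaccinated × rise, where 0.90 is the share without influenza.
- Low: 2476.8 × 0.50 × 0.02 × 0.30 = 7.4
- Middle: 2476.8 × 0.80 × 0.05 × 0.50 = 49.5
- High: 2476.8 × 0.80 × 0.20 × 0.70 = 277.4

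The consequences, taking all 275.2 true cases as detected:

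| | Low | Middle | High |
|---|---|---|---|
| False share, F/(275.2 + F) | 2.6% | 15.3% | 50.2% |
| Apparent influenza rate, (275.2 + F)/2752 | 10.3% | 11.8% | 20.1% |
| Apparent sensitivity, 0.80 × 275.2/(275.2 + F) | 77.9% | 67.8% | 39.8% |
| A 10-point difference, 10 × 275.2/(275.2 + F) | 9.7 | 8.5 | 5.0 |

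The 80% is the QuickVue sensitivity in Section 1.6; that row applies only when serology is in the reference. The 10 points are the 5% to 15% isolation improvement of Section 7.4, with no difference between groups assumed in the false cases. Infection after the index admission is not in these counts and would add to them.

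**4. No seasonal weighting.** Vaccination may cluster in autumn, but the documents do not say so. The autumn share also depends on the calendar used: September to November is 3 × 91 = 273 of the 666 days behind the 2752 (41%), but 3 of the 10 enrolment months in Section 5.1 (30%). The range in step 3 therefore uses no autumn share.

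**The case against.** The strongest reply is that the criterion is not mechanical. Serology has to indicate infection, and the four-fold rise is only an example, so a laboratory could discount a known vaccine response. Vaccination before admission is at least partly recorded, and an analysis plan not shown here could use it. An inpatient dose might surface among newly prescribed drugs (Section 6.2.2), and a dose after discharge might be volunteered as an extra medicine. These points stand as limits on certainty. They do not close the gap: judgement cannot discount a vaccination that nobody asked about, and no wording deals with infection after the index admission.

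Three stronger readings are tempting and are not supported.
- A reader might infer that every vaccinated patient with a rise becomes an influenza case by rule. The wording supports only that such patients can be so counted.
- A reader might infer that the main comparisons or all accuracy results are distorted. Length of stay, quality of life and cost are compared first in all patients. Objective 1 (Section 2.1) and Section 7.6 set the tests against traditional culture or laboratory methods. Serology is named as a further comparator in Section 7.5.3.
- A reader might infer bias towards one group. Groups are randomised and later vaccination is unlikely to depend on group, so the expected effect is dilution.

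The RSV example concerns another virus and does not contradict the influenza criterion. It does need reconciling with the day 10–90 draw, because the same serum serves both.

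Timing also matters. This is Version 6, dated 26/11/2007, and enrolment was scheduled from September 2005. A new question cannot reach patients already sampled.

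**Conclusion.** The point holds as a gap in the case definition and in data collection. Serology alone suffices, the window is open to day 90, vaccination after admission has no item of its own, and the baseline record is not used. Patients without influenza at the index admission can therefore enter the influenza subsets, the influenza admission rate and any accuracy estimate that uses serology.

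The text gap is certain; its size is not. The illustration runs from negligible (3% of influenza positives) to severe (50%), with a middle case of 15%, and every input beyond 2752 and 10% is assumed. It shows why the question should be settled and does not estimate the error. An analysis plan alone cannot repair it fully, because the vaccination data needed to identify the affected patients are not planned.

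**What to change.** 1. In Section 7.3, count a serology-only rise as influenza only when the convalescent serum falls within one stated interval. Reconcile that interval with the day 10–90 draw in Sections 4.1 and 6.2.12 and with the RSV example.
2. In the same section, do not count a serology-only rise when influenza vaccine is recorded shortly before admission or between the sera, with the look-back stated. Add one CRF line asking for the vaccine date at the convalescent draw, for patients still to be sampled.
3. For all patients, including those already enrolled, repeat the influenza-subset, admission-rate and serology-based accuracy analyses without serology-only positives. This needs no new data.

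The cost is a short amendment to Section 7.3, one CRF question at an existing contact and one extra set of analyses. The downside is the loss of some true serology-only cases. Their number depends on when within days 10–90 the samples were drawn, which the documents do not say, so late samples should be tabulated before the interval is fixed, without reference to results by group.

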#### **RSV positive** Patients will be considered RSV positive if:

The multiplex PCR is positive, and/or

- Viral culture is positive, and/or
- Serology results indicate RSV infection (e.g., ≥4-fold increase in RSV antibodies from Day 1 to Day 30).

S. pneumoniae positive Patients will be considered influenza positive if:

- The Binax NOW S. pneumoniae antigen test is positive, and/or
- Blood culture is positive, and/or
- Sputum culture is positive, AND the sputum sample is macroscopically purulent, AND the sputum sample reveals increased numbers of polymorphonuclear leucocytes, AND the Gram stain is positive, AND there is moderate-to-high amounts of growth, according to criteria used by the laboratory.

Evaluations will be based on: (i) populations whose cardio-pulmonary illness is confirmed as due to influenza, RSV or *S. pneumoniae*, and (ii) the study groups comprising all people who are investigated by the different strategies under investigation (rapid near patient tests, *versus* rapid molecular diagnosis, *versus* conventional laboratory tests).

#### 7.4 Statistical power

Statistical power has been estimated for one laboratory and two clinical endpoints for the elderly population only.

#### 1. Diagnostic accuracy

Assuming that the average sensitivity/specificity of the tests is 80%[90%] then allowing for a 20% dropout rate, a sample of 2752 (2000 i.e. only 2 winters) elderly patients randomised into the trial would enable the sensitivity/specificity to be estimated to within, i.e. 2SE, 7.6% (8.9%) [5.7% (6.7%)] for a disease prevalence of 10%, and 5.4% (6.3%) [4.0% (4.7%)] for a disease prevalence of 5%.

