- Based on the above, we expect to recruit 747 participants with pneumonia, of whom at least one third (n=249) should have *S. pneumoniae* infection. Of these, ~83 should be randomly allocated to the rapid near patient test (Binax NOW); the remainder will be randomised to the group tested by traditional methods. Thus the speed of diagnosis, impact of early diagnosis on prescribing, clinical outcomes, and costs will be assessed in groups having an estimated 83 and 166 subjects. However, as identical sample sets will be taken from each participant, the diagnostic accuracy of the tests will be assessed in all 249 subjects. The number of cases of *S. pneumonaie* infection that are likely to be identified among the anticipated 649 (556 +93) participants with unspecified acute lower respiratory tract infections is unknown, but their occurrence will add to the pool of cases for studies of diagnostic accuracy.
- On the basis of the Rochester study, we expect that 10% of the 2752 elderly (≥65 years) participants will have influenza A or B. Of the 275, one third (~92) will be allocated to the QuickView near patient influenza immunoassay; one third will be allocated to the rapid molecular group; the remainder will be allocated to the group tested by traditional methods. Identical sample sets will be taken from each individual, so the diagnostic accuracy of the tests will be assessed in all 275 subjects.
- Similarly, we expect that 5% of the 2752 elderly (≥65 years) participants will have RSV A or B. Of the 138, one third (~46) will be allocated to the rapid molecular group; the remainder (~92) will be allocated to the group tested by traditional methods. We expect that very few of these will be found

positive by the routine tests employed. Identical sample sets will be taken from each individual, so the diagnostic accuracy of the tests will be assessed in all 138 subjects.

While the numbers of patients with influenza and RSV who are allocated to the 'rapid' near patient or molecular tests are comparatively small (~92 + ~46 per elderly group, plus cases occurring in the 18-64-year-olds), the impact of a 'viral' infection (RSV or influenza) infection on patient isolation, antimicrobial prescribing, and clinical outcomes may be compared using a larger combined group – i.e.,

Elderly

Rapid influenza & RSV (i.e., Quickview + molecular tests) n=(92+92+46)=230Traditional influenza & RSV n=(92+46+46)=184

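### The diagnostic precision figures in Section 7.4 have their two prevalence labels exchanged, and they are sensitivity figures that are also offered for specificity

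*Protocol*

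**What the plan says.** Section 7.4, item 1, assumes an average sensitivity/specificity of 80%, with 90% as the alternative in square brackets. It takes "a sample of 2752 (2000 i.e. only 2 winters) elderly patients randomised into the trial", "allowing for a 20% dropout rate", and states that this "would enable the sensitivity/specificity to be estimated to within, i.e. 2SE", the following half-widths: "7.6% (8.9%) [5.7% (6.7%)] for a disease prevalence of 10%, and 5.4% (6.3%) [4.0% (4.7%)] for a disease prevalence of 5"%. Round brackets refer to 2000 patients. The Statistical power part of the synopsis carries the same figures with the same prevalence labels.

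Section 7.1 shows which infection each prevalence stands for. For influenza, "we expect that 10% of the 2752 elderly (≥65 years) participants will have influenza A or B". For RSV, "we expect that 5% of the 2752 elderly (≥65 years) participants will have RSV A or B". It also makes clear that accuracy is not split by randomised group. For influenza it says: "Identical sample sets will be taken from each individual, so the diagnostic accuracy of the tests will be assessed in all 275 subjects", and it says the equivalent for the 138 expected RSV cases.

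**The concern.** Sensitivity is estimated among patients who have the infection. If prevalence falls from 10% to 5% in a sample of fixed size, the number of such patients halves and the half-width grows by a factor of √2. The text has it shrinking, from 7.6% to 5.4% in the leading case. That suggests the labels are the wrong way round.

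The sentence also gives one set of figures for sensitivity and specificity together. Specificity is estimated among the 90–95% of patients without the infection, so it has a much larger denominator and hardly depends on which prevalence applies.

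Diagnostic accuracy is research objective 1 in Section 2.1. Section 7.4 covers one laboratory and two clinical endpoints, so this sentence is the only planned precision given for that objective. If it is wrong, a reader judging whether the trial can characterise the RSV test, which has the fewest expected cases, is given too favourable a figure. The same reader would be misled about the 2000-patient scenario, which shows what two winters alone would deliver.

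**Working it through.** **Inputs, all from Section 7.4, item 1.** Sensitivity or specificity p = 0.80 [0.90]; N = 2752 (2000); 20% dropout, leaving 0.8 × 2752 = 2201.6 (0.8 × 2000 = 1600) patients; half-width = 2SE; prevalence 10% or 5%.

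**Sensitivity.** Half-width = 2 × √[p(1 − p) / (0.8 × N × prevalence)].

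| N | Prevalence | Diseased | 2SE at 80% | 2SE at 90% | Printed at this prevalence |
|---|---|---|---|---|---|
| 2752 | 10% | 220.2 | 5.39% | 4.04% | 7.6% [5.7%] |
| 2752 | 5% | 110.1 | 7.62% | 5.72% | 5.4% [4.0%] |
| 2000 | 10% | 160 | 6.32% | 4.74% | 8.9% [6.7%] |
| 2000 | 5% | 80 | 8.94% | 6.71% | 6.3% [4.7%] |

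For example, with N = 2752, p = 0.80 and prevalence 10%: 2 × √(0.16 / 220.2) = 5.39%. All eight printed values appear in the table to one decimal, each against the other prevalence.

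**Working backwards.** The number of diseased patients implied by a half-width h is 4p(1 − p)/h².

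- The printed 7.6% at 80% implies 0.64 / 0.076² = 110.8 patients, and 110.8 / 2201.6 = 5.0% prevalence. It is labelled 10%.
- The printed 5.4% at 80% implies 0.64 / 0.054² = 219.5 patients, and 219.5 / 2201.6 = 10.0% prevalence. It is labelled 5%.
- Over all eight figures, the set labelled 10% implies 5.0–5.1% and the set labelled 5% implies 10.0–10.2%.

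**Other readings of the inputs.** For N = 2752 and p = 0.80, the half-widths at 10% and 5% prevalence would be:

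| Variant | 10% | 5% |
|---|---|---|
| 1.96 SE in place of 2SE | 5.28% | 7.47% |
| No dropout | 4.82% | 6.82% |
| Dropout as N/1.2 | 5.28% | 7.47% |
| One third of the sample | 9.34% | 13.21% |
| Two thirds of the sample | 6.60% | 9.34% |

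None gives the printed pair under the printed labels. Each rescales both columns together, so none can make the 5% figure the smaller.

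**Specificity.** Half-width = 2 × √[p(1 − p) / (0.8 × N × (1 − prevalence))].

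| N | Prevalence | Non-diseased | 2SE at 80% | 2SE at 90% |
|---|---|---|---|---|
| 2752 | 10% | 1981.4 | 1.80% | 1.35% |
| 2752 | 5% | 2091.5 | 1.75% | 1.31% |
| 2000 | 10% | 1440 | 2.11% | 1.58% |
| 2000 | 5% | 1520 | 2.05% | 1.54% |

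Between the two prevalences, specificity half-widths differ only by √(0.95/0.90) = 1.03. The printed sets differ by 7.6/5.4 = 1.41 up to 6.7/4.7 = 1.43, which is √2 within rounding. That is the pattern of a denominator made up of diseased patients only. The printed values are about three times (5.4/1.75 = 3.1) to four times (7.6/1.80 = 4.2) the specificity half-widths at their stated prevalences.

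**The case against.** The best case for leaving this as a minor point is that nothing in the design depends on it. The figure of 2752 comes from admissions data and recruitment fractions in Section 7.1, and precision is reported for that number afterwards. No target half-width is set, so none is missed once the labels are corrected. Section 7.6 provides for 95% confidence intervals with the accuracy estimates, and these will show the precision actually achieved. All of that stands. It limits the consequence to what a reader is told to expect, but does not make the sentence right.

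On specificity, one can say that an estimate good to about 1.8% is certainly within 5.4% or 7.6%, so the sentence is a loose bound that promises nothing the design cannot deliver. This has some force: nobody is led to expect more specificity precision than they will get. But the text defines the figures as 2SE, and read that way they are not the 2SE of specificity. The specificity part is therefore a real but secondary fault.

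The overstatement for RSV concerns sensitivity only. For specificity the printed figures are too wide at both prevalences.

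**Conclusion.** The sentence is wrong as written, in Section 7.4 and in the synopsis. The two prevalence labels are exchanged. At 80% sensitivity with 2752 patients, RSV is printed as ±5.4 points where the inputs give ±7.6. The printed half-width is about 29% too small ((7.6 − 5.4)/7.6), and the true interval is 1.41 times as wide. With 2000 patients the RSV figure is ±8.9, not ±6.3. Influenza is misstated in the opposite direction by the same amounts. Separately, none of the eight figures is a specificity half-width; those lie between about 1.3% and 2.1%.

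This rests on the protocol's own inputs, a simple binomial standard error, disease status taken as known, and all randomised patients remaining after dropout contributing to accuracy, as Section 7.1 says. The match on all eight figures leaves little doubt about the formula used. Sample size, recruitment and analysis methods do not change.

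**What to change.** In Section 7.4, item 1, and in the Statistical power part of the synopsis, exchange the two prevalences, restrict the existing figures to sensitivity, and add specificity with its prevalence stated. For N = 2752 (2000) and an assumed value of 80% [90%], the 2SE figures are:

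- Sensitivity, prevalence 10% (influenza): 5.4% (6.3%) [4.0% (4.7%)].
- Sensitivity, prevalence 5% (RSV): 7.6% (8.9%) [5.7% (6.7%)].
- Specificity, prevalence 10%: 1.8% (2.1%) [1.3% (1.6%)].
- Specificity, prevalence 5%: 1.7% (2.1%) [1.3% (1.5%)].

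The cost is a rewording of one sentence in two places. No design element or analysis needs to change.
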